#### 8.1.8 **Drug procurement and ordering:**

Open-label alisertib will be provided free of charge to patients by Takeda/Millennium Pharmaceuticals, Inc.

Each institution will order the drug through drug suppliers. (See Pharmacy Manual for order form.)

NOTE: Local drug destruction may occur if the site provides a copy of their local drug destruction policy to the sponsor (Mayo Clinic) and the respective drug suppliers (Takeda/Millennium).

#### 8.1.9 **Nursing Guidelines:**

8.1.9.1 Cytopenias have been seen with this agent. Monitor CBC and instruct patients to report any signs or symptoms of infection and/or abnormal bruising or bleeding to the study team.

8.1.9.2 GI side effects, including abdominal pain, diarrhea, dyspepsia, nausea, and vomiting have been seen. Treat symptomatically and assess for effectiveness.

8.1.9.3 Warn patients that they may experience somnolence, confusion or memory loss. Patient should be instructed not to operate a motor vehicle,

heavy machinery or participate in other activities that require mental sharpness until they know how this agent affects them.

- 8.1.9.4 Instruct patients that they may experience alopecia.
- 8.1.9.5 Monitor LFTs. Report increases in AST, ALT, bilirubin, GGT and Alk Phos to MD. Rarely hepatic veno-occlusive disease is seen.
- 8.1.9.6 Patients may experience palmar plantar erythrodysesthesia (hand-foot syndrome). Instruct patients to report any redness, pain, or skin issues of the hands or feet to the study team.
- 8.1.9.7 Alisertib can be administered regardless of the timing of food, unless otherwise specified. BID dosing should be taken every 12 hours and must be separated by at least 6 hours. Additionally doses should be swallowed with 250 mL (about 1 cup) of water and vomited doses should not be made up.
- 8.1.9.8 Neutralizing antacids should not be taken until 2 hours after alisertib is administered.
- 8.1.9.9a Gloves and protective garments should be worn during preparation and when dispensed in the clinic.
- 8.1.9.9b Do not open, crush or manipulate the pills in any way.
- 8.1.9.9c Alisertib can be given regardless of meals, unless the protocol dictates otherwise. Pills should be taken with at least 250 ml (1 cup) of water. Vomited doses should not be made up. Instruct patients that they should take their next dose at the regularly scheduled time.

## 8.2 Fulvestrant (Faslodex®)

Fulvestrant is commercially available.

### 8.2.1 Background

Fulvestrant is an estrogen receptor antagonist. Fulvestrant competitively binds to estrogen receptors on tumors and other tissue targets, producing a nuclear complex that causes a dose-related down-regulation of estrogen receptors and inhibits tumor growth.

### 8.2.2 Formulation, preparation and storage

Commercially available for injection as: Injection, solution: 50 mg/mL (5 mL) [contains benzyl alcohol, benzyl benzoate, castor oil, ethanol 10% w/v]

### 8.2.3 Preparation and storage

Refer to package insert for complete preparation and dispensing instructions. Store in original carton under refrigeration at 2°C to 8°C (36°F to 46°F). Protect from light.

### 8.2.4 Administration

Refer to the treatment section for specific administration instructions. Administer IM only; do not administer IV, SubQ, or intra-arterially. Administer 500 mg dose as two 5 mL injections (one in each buttocks) slowly over 1-2 minutes per injection.

### 8.2.5 Pharmacokinetic information

**Distribution:**  $V_d$ : ~3-5 L/kg

**Protein binding:** 99%; to plasma proteins (FLDL, LDL and HDL lipoprotein fractions)

**Metabolism:** Hepatic via multiple biotransformation pathways (CYP3A4 substrate involved in oxidation pathway, although relative contribution to metabolism unknown); metabolites formed are either less active or have similar activity to parent compound.

**Half-life elimination:** 250 mg: ~40 days

**Excretion:** Feces (~90%); urine (<1%)

### 8.2.6 Potential Drug Interactions

**Cytochrome P450 Effect: Substrate** of CYP3A4 (minor). There are no known interactions where it is recommended to avoid concomitant use.

### 8.2.7 Known potential toxicities

Consult the package insert for the most current and complete information.

#### **Common known potential toxicities, >10%**

Endocrine & metabolic: Fertility; Hot flushes

Hepatic: Alkaline phosphatase increased, transaminases increased

Local: Injection site pain

Neuromuscular & skeletal: Joint disorders

#### **Less common known potential toxicities, 1% - 10%**

Cardiovascular: Ischemic disorder

Central nervous system: Fatigue, headache

Gastrointestinal: Nausea, anorexia, vomiting, constipation, weight gain

Genitourinary: Urinary tract infection

Neuromuscular & skeletal: Bone pain, arthralgia, back pain, extremity pain, musculoskeletal pain, weakness

Respiratory: Cough, dyspnea

#### **Rare known potential toxicities, <1% (Limited to important or life-threatening)**

Angioedema, hypersensitivity reactions, leukopenia, myalgia, osteoporosis, thrombosis, urticaria, vaginal bleeding

## 8.2.8 Drug procurement and ordering

Commercial supplies. Pharmacies or clinics shall obtain supplies from normal commercial supply chain or wholesaler.

## 8.2.9 Nursing Guidelines

- 8.2.9.1 Rarely a blood-tinged vaginal discharge has been reported infrequently during therapy. Advise patients that this is a possibility and that studies have shown no effects on vagina or endometrium.
- 8.2.9.2 Monitor LFTs based on protocol requirements. Report increased LFTs to treating physician.
- 8.2.9.3 Hot packing the injection site for a short while after injection may prevent the possible bruising, tenderness, and/or erythema at the IM injection site.
- 8.2.9.4 It is recommended that pregnancy be avoided during treatment. Instruct patient and partner on adequate methods of birth control, if needed.
- 8.2.9.5 Instruct patient to report any signs or symptoms of blood clots. Patients with calf tenderness or burning, and/or chest pain (pulmonary embolus) should be evaluated by a physician immediately.
- 8.2.9.6 Warn patient of possible hot flashes. Assess severity and discuss non-hormonal treatments with treating physician. Assess treatment for efficacy.
- 8.2.6.7 May cause mild GI symptoms (nausea, anorexia, vomiting, constipation). Treat symptomatically and monitor for effectiveness of intervention.

## 9. CORRELATIVE/SPECIAL STUDIES

### 9.1 Body Fluid Biospecimens

#### 9.1.1 Summary of the blood biospecimen collection schedule

9.1.1.1 All Patients					
	Cycle 1, Day 1 prior to start of treatment (Baseline)	At the end of Cycle 1 (prior to start of Cycle 2)	At time of disease progression	Submit to:	Shipping/storage instructions
CTC	One 10 mL blood sample collected in a CellSave® tube and one 10 mL blood sample collected in an AccuCyte tube	One 10 mL blood sample collected in CellSave® tube and one 10 mL blood sample collected in an AccuCyte tube	One 10 mL blood sample collected in CellSave® tube and one 10 mL blood sample collected in an AccuCyte tube	BAP freezer Mayo Clinic	Samples should be kept at ambient temperature after collection and during shipping. Specimens must arrive at Mayo within 72 hours of collection.
cfDNA	Two 10 mL blood samples collected in Streck® tubes	Two 10 mL blood samples collected in Streck® tubes	Two 10 mL blood samples collected in Streck® tubes	BAP freezer Mayo Clinic	Samples should be kept at ambient temperature after collection and during shipping. Specimens must arrive at Mayo within 72 hours of collection.
SNP	One 6 mL blood sample collected in a K2 EDTA tube. Gently invert tube 6-8 times - Do not centrifuge	-	-	BAP Mayo Clinic	Upon processing, refrigerate until shipment; ship refrigerated

9.1.1.2 For those patients with crossover from alisertib to the combination of alisertib and fulvestrant					
	Cycle 1, Day 1 of alisertib and fulvestrant, (if missed at time of progression on alisertib)	At the end of Cycle 1 of alisertib and fulvestrant	At time of disease progression on alisertib plus fulvestrant	Submit to:	Shipping/storage instructions
CTC	One 10 mL blood sample collected in a CellSave® tube and one 10 mL blood sample collected in an AccuCyte tube	One 10 mL blood sample collected in a CellSave® tube and one 10 mL blood sample collected in an AccuCyte tube	One 10 mL blood sample collected in a CellSave® tube and one 10 mL blood sample collected in an AccuCyte tube	[REDACTED]	Samples should be kept at ambient temperature after collection and during shipping Specimens must arrive at Mayo within 72 hours of collection
cfDNA	Two 10 mL blood samples collected in Streck® tubes	Two 10 mL blood samples collected in Streck® tubes	Two 10 mL blood samples collected in Streck® tubes	[REDACTED]	Samples should be kept at ambient temperature after collection and during shipping Specimens must arrive at Mayo within 72 hours of collection

See Lab Manual for detailed instructions

Ship blood samples to:

Samples should be collected and shipped Monday – Thursday. However, if the subject can only be seen on Fridays, please ensure that Saturday delivery is marked clearly on the shipping boxes.

### 9.1.2 Methods

#### Circulating Tumor Cell Capture and Phenotyping

The relative abundance of CTCs in the peripheral blood has strong correlation with tumor recurrence and distant metastases in both early stage and advanced breast tumors. We will prospectively isolate CTCs from blood specimens collected from study participants at three time points for phenotypic and possibly genotypic analyses.

One 10 mL blood sample will be collected in the CellSave® Preservation Tube for CTC isolation using the Veridex CellSearch™ system (Janssen; Raritan, NJ). CellSave® contains an optimized preservative that stabilizes cells for up to 96 hours at room temperature. The CellSearch™ system [REDACTED] allows for the

immunomagnetic selection, fluorescence staining, concentration, and enrichment of CTCs for enumeration and analysis. The FDA cleared process uses the CellSearch™ Epithelial Cell Kit, which contains anti-EpCAM (epithelial cell adhesion molecule) Ferrofluid, a fluorescent nucleic acid dye (DAPI), and fluorescently labeled monoclonal antibodies specific for leukocytes (CD45) and epithelial cells (cytokeratins 8, 18, and 19) to identify CTCs as those that are cytokeratin positive, DAPI positive, and CD45 negative with the appropriate morphology. At least two-thirds of patients with metastatic breast cancer have >1 CTC per 7.5 mL blood assayed with this technology, and the enumeration of CTCs relative to a threshold of 5 CTCs per 7.5 mL blood is associated with clinical outcomes in this patient population. The standard process has been modified to allow for CTC retrieval and subsequent assessment for additional protein markers of interest (e.g., Aurora A kinase, ER, p-SMAD5, and p-SOX2).

CTCs vary in the degree of EpCAM expression, so malignant cells in the circulation may be missed by the CellSearch technology. Toward that end, other methodologies that do not rely on EpCAM for capture are now available. Therefore, a second 10 mL blood sample will be collected in the AccuCyte® Blood Collection Tube for CTC isolation using the AccuCyte® Platform (RareCyte; Seattle, WA). The blood collection tube contains an optimized preservative that stabilizes cells for up to 96 hours at ambient temperature. The AccuCyte® Platform [REDACTED] is a comprehensive, reproducible, and highly sensitive platform for enriching, identifying, and isolating CTCs for downstream molecular analyses (ref: Campton DE et al. BMC Cancer 2015. 15:360.). The system relies on density gradient centrifugation and allows for virtually complete harvesting of the buffy coat into a small volume for application to a microscopic slide without cell lysis or washing. Immunofluorescent staining for selected markers (e.g., cytokeratins, EpCAM, DAPI, CD45, HER2, ER, Aurora A kinase, p-SMAD5, and p-SOX2) is used for the efficient positive and negative identification of CTCs via automated scanning digital microscopy and image analysis. An integrated device provides for mechanically precise CTC retrieval for advanced genomic analyses, including next generation sequencing, on single or pooled CTCs.

## 9.2 Pathology Considerations/Tissue Biospecimens

### 9.2.1 Summary Table of Research Tissue Specimens to be Prospectively Collected for this Protocol

**Note:** Only send registration tissue if the patient qualifies for the study

Correlative Study (Section for more information)	Mandatory or Optional	Type of Tissue to Collect	Slides, Core, etc. (# of each to submit)	Pre-registration (biopsy) 	Upon completion of Cycle 1 	At Disease Progression	At disease progression after combination (ARM 1 ONLY)	Process at site?	Temperature Conditions for Storage /Shipping
Aurora A Kinase, SMAD5, SOX2 and ER $\alpha$ Expression	Mandatory	Formalin Fixed Paraffin Embedded	10 unstained slides (2 to 4 cores)	X	X	X	X	Yes	Ambient via Pathol coordinator
Real time PCR for ER target genes	Mandatory	Flash Frozen	1 core (3-4 mm)	X	X	X	X	Yes	Pathol coordinator
Patient Derived Xenograft	Mandatory for Mayo Clinic Subjects Only	Fresh	2 cores	X		X		Yes	In PBS or DMEM medium at room temperature within 30 minutes between the time when samples are obtained and the time samples are delivered to the xenograft team

[figure not shown]
Correlative Study (Section for more information)	Mandatory or Optional	Type of Tissue to Collect	Slides, Core, etc. (# of each to submit)	Pre-registration (biopsy) 	Upon completion of Cycle 1 	At Disease Progression	At disease progression after combination (ARM 1 ONLY)	Process at site?	Temperature Conditions for Storage /Shipping
LMW-E expression (MDACC)	Mandatory	Formalin Fixed Paraffin Embedded	1-2 unstained slides	X	X	X	X	Yes	MDACC Contact

1. If pre-registration biopsy is attempted and either aborted or insufficient tissue is obtained, the patient may still be eligible. In this case, the site may submit slides from archival specimens for central lab determination of ER status for patient stratification. Refer to Lab Manual for detailed instructions.  
NOTE: If biopsy does not obtain tissue AND no archived tissue is available for Central Laboratory review, patient is not eligible. A repeat biopsy may be attempted at the discretion of the treating physician and patient.
2. Performed once up to 4 days prior to the start of Cycle 2. Must be performed prior to initiation of treatment for Cycle 2.

Ship frozen tissue samples to:

Ship tissue slides/cores to Mayo Clinic Cancer Center Operations Office

## 9.2.2 Correlative Tumor Tissue Collection

### **In All Subjects:**

#### 9.2.2.1 Selection of metastatic lesion site for biopsy

A lung lesion should only be pursued for research biopsy in the event there is no other site of disease amenable to biopsy. If a lung lesion is the only site of disease amenable to biopsy, then peripheral lesions should be carefully selected due to risk of pneumothorax. Biopsy of central lesions is not advised. If a lung lesion is the only site of disease amenable to biopsy, then only 2 of the 3 mandatory biopsies will be required-- the pre-treatment/baseline and post-Cycle 1 biopsies. The biopsy at disease progression will not be required, nor is it optional.

#### 9.2.2.2 Two cores will be obtained with each research biopsy

One core will be formalin-fixed, paraffin-embedded (FFPE) and the tissue block will be sent to the Mayo Clinic Pathology Research Core (PRC). Sections (5 micron) will be cut from the tumor tissue block to obtain 10 unstained slides that contain at least 75% tumor tissue. These slides will be used for IHC assessment of the following biomarkers: Aurora A Kinase, SMAD5, SOX2 and ER $\alpha$ . One to two slides will be submitted to the laboratory of co-investigator, [REDACTED] for evaluation of both full length (nuclear) and LMW cyclin E (cytoplasmic) by IHC in FFPE tissue biospecimens.

One core will be flash frozen and sent to the Mayo Clinic PRC. RNA will be isolated from the biospecimen. Following cDNA synthesis, the expression levels of well characterized ER $\alpha$  target genes (TFF1, Progesterone Receptor, and amphiregulin) will be assessed by quantitative real-time PCR. Results will be expressed relative to an internal control housekeeping gene (TBP).

#### 9.2.2.3 Aurora A Kinase, SMAD5, SOX2 and ER $\alpha$ Expression

Antibodies to detect total Aurora-A kinase, ER $\alpha$ , SMAD5 and SOX2, and phospho-SMAD5 and phospho-SOX2, are available through the Mayo PRC or will be purchased from Cell Signaling Technology, Boston, MA, USA and processed according to package insert. The phospho antibodies will be optimized through standard procedure with the PRC. Normal human breast tissues from reduction mammoplasty will serve as negative control and triple-negative breast tumor tissues as positive control. The intensity of biomarkers expression will be scored as strong, moderate, or weak-to-none using digital image analysis employing an innovative *ImageScope viewing software (Leica Biosystems)* to accurately measure Aurora-A, SMAD5, SOX2 and ER $\alpha$  nuclear expression in breast tumor clinical samples.

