### 2.3 Correlative Research

- 2.3.1 To assess the changes in Aurora A kinase, SMAD5 and SOX2 expression and phosphorylation in tumor tissue after first cycle of assigned treatment
- 2.3.2 To assess the changes in ER expression and function in tumor tissue after the first cycle of assigned treatment

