### 3.5 Rationale to Allow Women with ER-negative Disease to Participate

It is feasible that women with a history of primary, operable breast cancer that is ER+ who endure metastatic relapse that is ER <10% or ER negative, may derive benefit from alisertib. This is known to occur in up to 20% of patients. The hazard of death in women with ER+ primary breast cancer whose recurrence is ER <10% or ER negative is 1.48 times (95% CI, 1.08 to 2.05) that of woman who retain ER+ at metastatic relapse. These tumors may be heavily comprised of the Aurora-A kinase over-expressing CD44+/CD24low/- ER $\alpha$ low/- BTICs that alisertib targets. In fact, alisertib may allow for reversion of the luminobasal phenotype and restoration of ER $\alpha$  expression, functional activity, and thus sensitivity to hormonal treatment.

[figure not shown]

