### 17.3 Stratification Factors

This study will use the Pocock and Simon dynamic allocation procedure to allocate an equal number of patients to each of the treatment strategies. This procedure will balance the marginal distributions of the stratification factors, clinical endocrine resistance and ER status, between these treatment strategies.

- Clinical Resistance to Endocrine Therapy:
  - 1= Primary endocrine resistance- recurrence within the first 2 years of adjuvant endocrine therapy, or progression within the first 6 months of initiating first-line endocrine therapy for MBC
  - 2= Secondary endocrine resistance- recurrence during Years 2-5 of adjuvant endocrine therapy (or within 12 months of completing adjuvant endocrine therapy) or progression occurring 6 or more months after initiating endocrine therapy for MBC.
- ER findings from registration biopsy
  - 1 = ER positive ( $\geq 10\%$  staining)
  - 2 = ER weakly positive (1 to 9.9% staining) or ER negative (0% staining)
- Prior therapy with a CDK 4/6 inhibitor (palbociclib, ribociclib or abemaciclib)
  - 1=yes

2=no

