### 17.4.4 Examination of changes in tumor biomarkers after one cycle of initial treatment

For each treatment arm, a Spearman rank correlation coefficient will be used to examine the association of maximum percentage of tumor shrinkage during treatment with the percent change after 1 cycle of treatment in AAK expressing cells, as well as percent changes after 1 cycle of treatment in tissue ER $\alpha$ , SMAD5, SOX2 expression and phosphorylation.

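### The research IHC in Section 9.2.2.3 names no valid positive control for ERα, and its three-level score cannot show a none-to-weak change or supply the percent change that Section 17.4.4 analyses

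*Combined protocol and SAP*

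**What the plan says.** Section 9.2.2.3 lists antibodies to total Aurora A, ERα, SMAD5 and SOX2, and to the phosphorylated forms of SMAD5 and SOX2. They are to be "processed according to package insert", and the phospho antibodies are to be optimised at the pathology core. The section then sets the controls without separating the markers: "Normal human breast tissues from reduction mammoplasty will serve as negative control and triple-negative breast tumor tissues as positive control". Expression is "scored as strong, moderate, or weak-to-none using digital image analysis", and the sentence goes on to name ERα among the markers measured this way.

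Objective 2.3.2 is "To assess the changes in ER expression and function in tumor tissue after the first cycle of assigned treatment". Section 17.4.4 correlates maximum tumour shrinkage with the percent change in Aurora A-expressing cells, "as well as percent changes after 1 cycle of treatment in tissue ER"α, SMAD5 and SOX2.

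**The concern.** A positive control must contain the target; otherwise a blank slide cannot be told apart from a failed stain. Triple-negative tumour may suit Aurora A, SMAD5 and SOX2, but it lacks ER.

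The score raises a separate problem. Section 3.5 justifies enrolling patients whose disease has lost ER on the ground that "alisertib may allow for reversion of the luminobasal phenotype and restoration of ER"α. In such a patient the first visible step would be from no staining to weak staining, and the lowest category puts both in one class. The score also leaves out the percentage of cells stained, which is how the protocol defines ER status elsewhere (Sections 1, 4.1.4, 6.1.2 and 17.3).

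At stake is the tissue evidence on ER re-expression, for which patients undergo a mandatory biopsy after Cycle 1.

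**Working it through.** **1. Control against marker.** Triple-negative means negative for ER among others. The protocol's own planning agrees: Section 1 expects 10% of patients with ER-negative metastatic disease, and Section 17.2 carries about 10% as triple-negative. Section 9.2.2.3 therefore names an ER-negative tissue as the positive control for a panel containing ERα. No other section names an ERα control.

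**2. Is ERα protein in tissue read any other way after Cycle 1?**

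| Read | Where | When | What it gives |
|---|---|---|---|
| Central ER | 11.1, 11.2, 17.3 | Pre-registration | Percent staining |
| PCR of ERα target genes | 9.2.1, 9.2.2.2 | Pre-registration, after Cycle 1, progression | ER function |
| Clinical ER re-check | 1, 6.1.2 | Progression, before crossover, if ER was below 10% | Percent staining against 10% |
| ER on circulating tumour cells | 2.4.2, 17.4.5 | Baseline and after Cycle 1 | Blood, exploratory |
| Research IHC | 9.2.1, 9.2.2.3 | Pre-registration, after Cycle 1, progression | Three-level intensity |

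Only the last row reads ERα protein in tissue after Cycle 1. No section repeats the percent-staining read on that biopsy.

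**3. Score against analysis.** None at baseline and weak after Cycle 1 both fall in weak-to-none, so the recorded change is zero. Nor does a category yield a percent change without arbitrary codes:

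- Coded 1, 2, 3: weak-to-none to moderate is (2 − 1)/1 = 100%, and moderate to strong is (3 − 2)/2 = 50%.
- Coded 0, 1, 2: the first is (1 − 0)/0, which is undefined, and the second is (2 − 1)/1 = 100%.

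The result depends on the coding, which the plan does not give.

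**4. The nearest stated figure.** Section 17.4.3 gives 90% power for a Spearman test of baseline ERα against the other markers, with n = 81, two-sided alpha 0.05 and a true correlation of 0.35.

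- Fisher z: power = Φ(atanh(0.35) × √(81 − 3) − 1.960) = Φ(0.3654 × 8.832 − 1.960) = Φ(1.267) = 0.898.
- Simulation with continuous markers (3,000 runs, bivariate normal): 0.900.
- The more conservative Spearman variances give 0.880.

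The stated 90% is reproduced. It treats the markers as continuous. The documents give no score distribution, so the loss from three levels is shown over assumed splits (weak-to-none/moderate/strong):

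| Assumed split | ERα alone on three levels | Both markers on three levels |
|---|---|---|
| one third each | 0.82 | 0.77 |
| 50/30/20 | 0.82 | 0.72 |
| 70/20/10 | 0.71 | 0.57 |

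This concerns the baseline correlation, not change after Cycle 1. It illustrates lost information and does not correct the stated power.

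**5. How many patients.** Baseline tissue: 0.90 × 90 = 81 (Section 17.4.3). ER-negative disease: 0.10 × 90 = 9 (Section 1).

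**The case against.** Four arguments deserve an answer.

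- **The control sentence may cover only the phospho antibodies**, because it directly follows the sentence on optimising them. That reading is possible but not the natural one: the sentence carries no such limit, and the next one again includes ERα. Processing to the package insert may in practice bring in a suitable ER control, but the protocol does not say so.
- **A numeric read is probably intended.** Section 9.2.2.3 uses digital image analysis, and Section 17.4.4 speaks of percent change, so the three levels may be only a summary. This is fair, and it makes the score problem partly a drafting mismatch. The numeric output still has to be named.
- **Grouping weak with none is the protocol's habit.** Section 17.3 puts 0% and 1 to 9.9% staining in one stratum, and Section 17.4.3 tests weak-or-no phosphorylated expression. Those groupings suit stratification and that test, not the measurement of change. Section 17.3 also classes percentage of cells, whereas Section 9.2.2.3 classes intensity, so one does not validate the other.
- **ER is measured in other ways.** This stands, and it limits the point. A reader might infer that ER restoration cannot be read at all. The documents do not support that: PCR covers ER function after Cycle 1, the crossover re-check uses percent staining, and a shift to moderate or strong would still register. A reader might also infer that every ERα run must fail, or be accepted only when ER-negative tumour stains. The documents state no run-acceptance rule, so neither follows.

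**Conclusion.** The point holds for one readout: ERα protein in tumour tissue after Cycle 1. As written, that read has no valid positive control, cannot distinguish none from weak, and is not on the scale that Section 17.4.4 needs. The conclusion assumes that the control sentence applies to the whole panel and that the three-level score is the recorded result.

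The size cannot be fixed. The 81 is patients with baseline tissue, so it is a ceiling and not a count of baseline and post-Cycle-1 pairs. The roughly 9 patients are all those expected to have ER-negative disease; only those who start at none by this assay could show a none-to-weak shift, and the documents do not size that subset. A reader might double the figure from the rate of up to 20% in Section 3.5 (0.20 × 90 = 18). That rate describes relapse with ER below 10% or negative in general, not the enrolment expectation.

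Only correlative work is affected. The primary endpoint, sample size, alpha and crossover eligibility do not depend on this assay. The correction is still worth making, because ER restoration is the trial's stated mechanism and the change is small.

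**What to change.** In Section 9.2.2.3:

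- Set the ERα controls separately. Name a known ER-positive breast tumour as positive control, and a known ER-negative tumour or a section without primary antibody as negative control. The documents do not say that reduction-mammoplasty tissue lacks ER, so the negative side needs naming too.
- From the same sections and image analysis, record percent positive cells and intensity as 0, 1+, 2+ or 3+ at baseline and after Cycle 1, so that none and weak are separate.

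In Section 17.4.4, state that this numeric read is the one analysed. Say also whether percent change means a difference in percentage points or a relative change, because a relative change is undefined when the baseline is zero.

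The three-level score can stay for the weak-or-no test in Section 17.4.3.

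The cost is a different control slide for one marker, slightly more image-analysis output and a few lines of text. No extra patient tissue is needed. If ERα slides have already been stained, the report should say which control was used.
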